3.3.2.2 Claims-based Health Care Resource Utilization and Costs

- **All-cause baseline health care resource utilization**—Binary indicators and counts of ambulatory (physician office and hospital outpatient) visits, ED visits, and inpatient stays will be calculated in the 12-month baseline period.
- **All-cause baseline health care costs**—Consumer Price Index-adjusted costs will be assessed for the 12-month baseline period. Costs will be calculated as total costs, pharmacy costs, and medical costs; medical costs include ambulatory (physician office and hospital outpatient) costs, emergency costs, inpatient costs, and other costs.
- **COPD-related baseline health care resource utilization**—Binary indicators and counts of ambulatory (physician office and hospital outpatient) visits, ED visits, and inpatient stays will be calculated in the 12-month baseline period. Utilization will be defined as COPD-related when a diagnosis code for COPD (Figure 2) is in the primary position.
- **COPD-related baseline health care costs**—Consumer Price Index-adjusted costs will be assessed for the 12-month baseline period. Costs will be calculated as total costs, pharmacy costs, and medical costs; medical costs include ambulatory (physician office and hospital outpatient) costs, emergency costs, inpatient costs, and other costs. Costs will be defined as COPD-related if the claim has a diagnosis code for COPD (Figure 2) in the primary position or is for a medication used to treat COPD. Codes for COPD treatment will be provided in the SAP (and will include those in Figure 3).

Payments from Medicare are estimated based on coordination of benefits information obtained by the health plan in its usual course of business. This study will incorporate the amounts estimated to be paid by other payers (i.e., Medicare) for a total paid or allowable amount^{xi}.

- **COPD exacerbations**—Whether the patient has evidence of a COPD exacerbation during the 12-month baseline period will be captured. The count of exacerbations will be presented. GSK's harmonized exacerbation definition will be used; the definition will be included in the SAP.
- **COPD exacerbation-related baseline health care costs**—CPI-adjusted costs will be assessed for the 12-month baseline period. Total costs (pharmacy + medical) will be reported. Costs will be attributed to an exacerbation per GSK's harmonized exacerbation definition.

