3.4.1 Primary Endpoint

- **Patient-reported symptom burden.** Scores will be presented from validated instruments measuring dyspnea (mMRC) and condition-related burden of illness (CAT). Mean total, summary, and/or domain scores and standard deviations will be presented for each scale/item (as described in Section 3.3.1.3). The proportion of patients with high and low symptom burden on both PRO measures will be calculated. Results will be presented for the overall study sample and by treatment cohort (FLUT/SAL or UMEC/VI).
- **Proportion of patients reporting COPD symptoms while treated with FLUT/SAL or UMEC/VI.** The proportion of patients who report COPD symptoms will be computed for survey respondents. Two calculations will be presented: the number of COPD patients who report COPD symptoms as measured by a CAT total score ≥ 10 , divided by the total number of respondents with a CAT total score; and the number of COPD patients with an mMRC score of 2-4, divided by the total number of respondents with an mMRC score. Results will be presented for the overall study sample and by treatment cohort.
- The mMRC and CAT instruments are included to correspond with current GOLD guidelines.

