3.4.2 Secondary Endpoint(s)

- **Baseline health care resource utilization and costs.** All-cause and COPD-related health care costs will be presented for the 12-month baseline period. Mean, median, and standard deviations will be presented for total costs and utilization and for each category of costs (i.e., pharmacy + medical, and the subcategories of medical costs as described in Section 3.3.2.2). Costs and counts will be presented overall and for the subset of patients utilizing the selected type of service. The proportion of patients receiving services for each type of service and the proportion of patients with non-zero costs for each type of cost will be calculated. Results will be presented for the overall study sample and may be stratified by relevant subgroups for analysis (e.g., by low versus symptom burden as measured by patient mMRC and CAT scores).
- **Patient clinical characteristics.** The proportion of patients with evidence of selected clinical characteristics will be presented. The top 20 claims-based comorbidities and up to 10 COPD-related comorbidities will be identified. The percent of patients with each condition will be identified. Mean and standard deviation will be calculated for the Quan-Charlson comorbidity score. Results will be presented for the overall study sample and may be stratified by relevant subgroups for analysis (e.g., by low versus high symptom burden as measured by patient mMRC and CAT scores).
- **Patient GOLD classification.** The proportion of patients in each GOLD category of symptom burden and exacerbation will be presented. The calculation will use count of COPD exacerbations during the baseline combined with CAT total score and mMRC score to create mutually exclusive counts for each category (A, B, C, D) (Section 10, Appendix 3).

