4.3 Descriptive Analyses of Survey and Claims Data

Administrative Claims Data

Health service utilization and costs for the baseline period will be identified and presented descriptively for all-cause and COPD-related total HCRU and costs. For dichotomous variables, N (%) will be presented. For continuous variables, means, standard deviations, medians, ranges, and percentiles will be presented as appropriate. Costs will be defined as costs to the health plan and estimated costs paid by Medicare; costs will not include costs to the patient (copays, deductibles). Detailed descriptions of cost and utilization measures are provided in 3.3.2.2.

Survey Data

All study variables will be analyzed descriptively. Numbers and percents will be provided for dichotomous and polychotomous variables. Relevant measures of centrality such as means and medians will be presented for continuous measures, as well as variance measures such as standard deviations and percentiles (e.g., p25, p75). Comparisons of demographic characteristics and outcome measures will be provided. Appropriate tests (e.g., t-test, Mann Whitney-U test, chi-square test) will be used based on the distribution of the measure. For example, a one sample t-test could be used to show difference from the sample mean on a given PRO (such as CAT score) as compared to an expected value (such as CAT scores among older adults from the published literature). Pearson correlation coefficients are utilized for bivariate comparisons of CAT total score and mMRC score with selected clinical and sociodemographic characteristics.

In addition to descriptive analyses of all survey variables, survey responders and non-responders will be compared on select demographic characteristics in order to assess the generalizability of the evaluable survey sample.

Primary Objective

In order to fulfill the primary objective, the proportion of patients with low and high symptom severity will be identified based on responses to the mMRC and CAT measures. Patients may be categorized into multiple levels of severity based on the distribution of responses to one or both measures (e.g., patients with a high degree of dyspnea per the mMRC score and severe symptom burden per the CAT score may be categorized as most severe for relevant analyses).

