Classification of symptom burden is based on established cutpoints for validated instruments. For the mMRC, scores ≥ 2 reflect high levels of dyspnea, and CAT scores >10 reflect high levels of COPD burden, with a 5-point difference between stable and exacerbating patients established during instrument validation^{xiii}. Correlation between these measures of symptom burden will be compared descriptively using t-tests.

Secondary Objectives

One secondary objective is to describe baseline all-cause, COPD-related, and exacerbation-related health care resource utilization, costs, and clinical characteristics. Using cross-tabulations and chi-square tests, we will describe characteristics of patients with high and low utilization and costs in terms of their symptom burden (e.g., mMRC and CAT scores), clinical characteristics (e.g., time since COPD diagnosis, treatment, comorbidity score, smoking history), and demographic and sociodemographic characteristics (age, gender, race, ethnicity, marital status, educational attainment, area of residence, and income level). Utilization and cost levels may be based on the distribution of scores among the survey sample and/or relevant literature.

The additional secondary objective is to describe patient GOLD classification. The proportion of patients in each GOLD category of combined symptom burden and exacerbation risk will be presented by treatment cohort. The calculation will use count of COPD exacerbations during the baseline combined with CAT total score and mMRC score to create mutually exclusive counts for each category (A, B, C, D)(see Section 10, Appendix 3).

Sensitivity Analysis

To assess whether differences are observed in patients based on their history of COPD exacerbations, sensitivity analysis will be conducted. This analysis will describe patient-reported symptom burden, demographic and sociodemographic characteristics, and baseline clinical characteristics for patients with and without claims-based evidence of exacerbations during the 12-month baseline period.

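### Symptom burden is linked to cost only through a chi-square test on a high/low split whose cut is not pre-specified; a full-scale analysis of data already held would be markedly more sensitive

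*Combined protocol and SAP*

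**What the plan says.** Section 4.3 sets out the aim of this part of the analysis: "One secondary objective is to describe baseline all-cause, COPD-related, and exacerbation-related health care resource utilization, costs, and clinical characteristics". It then gives the method: "Using cross-tabulations and chi-square tests, we will describe characteristics of patients with high and low utilization and costs in terms of their symptom burden". The same sentence goes on to list clinical and sociodemographic characteristics, most of them categorical. On where high ends and low begins, it says only: "Utilization and cost levels may be based on the distribution of scores among the survey sample and/or relevant literature". No quantile, dollar value or visit count is given.

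Other parts of the protocol bear on the same link:

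- Section 3.3.2.2 keeps the underlying measures in usable form: "Binary indicators and counts of ambulatory (physician office and hospital outpatient) visits, ED visits, and inpatient stays will be calculated". Costs are held as continuous amounts.
- Section 3.4.2 plans full-scale summaries: "Mean, median, and standard deviations will be presented for total costs and utilization and for each category of costs". Breaking these down by symptom burden is optional, and no test is named for it.
- Section 4.3, under Survey Data, plans correlations: "Pearson correlation coefficients are utilized for bivariate comparisons of CAT total score and mMRC score with selected clinical and sociodemographic characteristics". Cost and utilization are not named there.
- Section 4.5 outlines two regression models, with CAT total score and mMRC score as the outcomes. Appendix 4 lists candidate covariates, which include counts of ambulatory visits, medication fills and exacerbations. It does not list cost, ED visits or inpatient stays.

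**The concern.** The synopsis rationale pairs patient-reported symptom burden with claims-based economic burden, and the Introduction says the study will inform on associations that include symptoms and economic characteristics. Yet the one firmly committed analysis joining symptoms to cost turns a continuous cost into two groups. A cross-tabulation also needs CAT, a 0-40 score, to be grouped. If mMRC is left as five grades, an ordinary chi-square ignores their order.

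Three things follow. A modest association is harder to detect than it need be, and a non-significant chi-square may be read as no association. The result can depend on a cut that is still open. And the table cannot say how cost changes per CAT point, which is the quantity a payer would want.

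The CAT grouping is itself unsettled. Section 4.3 says "scores ≥ 2 reflect high levels of dyspnea, and CAT scores >10 reflect high levels of COPD burden", whereas section 3.4.1 counts patients who "report COPD symptoms as measured by a CAT total score ≥ 10". A patient scoring exactly 10 changes group between the two. An analysis on the full CAT scale does not depend on that choice.

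**Working it through.** **Sample size.** Section 3.5 gives 385 per cohort. With n = z² p(1−p)/d², z = 1.96, p = 0.5 and d = 0.05: 3.8415 × 0.25 / 0.0025 = 384.15, rounded up to 385. This reproduces, and two cohorts give 770. It is a precision figure for one proportion. The documents attach no power, correlation or cost SD to the symptom-cost analysis, so everything below rests on stated assumptions.

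**Assumptions.** Symptom score and log cost are bivariate normal, the association is weak, n = 770, and tests are two-sided at 5%. Zero costs and residual skew would change the exact values.

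**Information kept after a cut.** Cutting a normal variable at quantile q keeps the fraction φ(z_q)² / [q(1−q)]. If both variables are cut, the two fractions multiply.

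| What is cut | Calculation | Kept | Lost | 770 acts like |
|---|---|---|---|---|
| Cost at median | 0.3989² / 0.25 | 0.637 | 36% | 490 |
| Cost at 75th percentile | 0.3178² / 0.1875 | 0.539 | 46% | 415 |
| Cost at 80th percentile | 0.2800² / 0.16 | 0.490 | 51% | 377 |
| Cost and symptoms, both at median | 0.637 × 0.637 | 0.405 | 59% | 312 |
| Cost at median, 70% high-symptom | 0.637 × 0.576 | 0.366 | 63% | 282 |
| Cost at 75th percentile, 70% high-symptom | 0.539 × 0.576 | 0.310 | 69% | 239 |

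If 80% of patients are high-symptom and cost is cut at the 75th percentile, 0.539 × 0.490 = 0.264 is kept and 74% is lost.

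**Power at an assumed correlation of 0.10.** Spearman on the full scales, by simulation, gives about 76%. For the 2x2 chi-square, the phi coefficient follows from the bivariate-normal cell probabilities, and the noncentrality is 770 × phi²:

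| Split | phi | Power |
|---|---|---|
| Both at median | 0.064 | 43% |
| Cost at median, 70% high-symptom | 0.061 | 39% |
| Cost at median, 80% high-symptom | 0.056 | 34% |
| Cost at 75th percentile, 70% high-symptom | 0.055 | 33% |
| Cost at 75th percentile, 80% high-symptom | 0.050 | 28% |

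Keeping the symptom score whole and cutting only cost gives about 60% at the median (t-test, simulated). Leaving an mMRC-like scale as five unordered categories against a median cost split gives about 35%, so using all five grades does not help unless their order is used.

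**Sensitivity to the correlation.** Over the splits in the table above:

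| Correlation | Spearman | 2x2 chi-square |
|---|---|---|
| 0.08 | about 56% | 20-29% |
| 0.10 | about 76% | 28-43% |
| 0.15 | about 98% | about 54-76% |
| 0.20 | above 99% | about 77-94% |
| 0.25 | above 99% | about 91-99% |

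The loss therefore matters most for weak associations and narrows from about 0.20 upward.

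**The case against.** The best case for the plan is that this is a profiling table. The secondary objective is to describe, section 3.6 gives hypotheses only for the primary objective, and estimating a symptom-cost association is not listed as an objective in section 2.2. That stands, and it limits the weight of the point. It does not remove it, because section 4.3 attaches a significance test to the table and the test will be read.

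Cross-tabulation and chi-square also suit most characteristics in that sentence, such as gender, race, marital status, education and income. That stands too: the point concerns the symptom scores against cost and utilization, not the rest of the table.

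A reader might infer that chi-square is the only planned link between symptoms and any utilization measure. The documents do not support that. The ambulatory-visit, medication-fill and exacerbation counts in Appendix 4 may enter the section 4.5 models uncut, although the final covariates are chosen later and the outcome may be dichotomized. The gap is clearest for cost, ED visits and inpatient stays.

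A reader might also infer that the cut will be taken from the data after they are seen. Section 4.3 allows the sample distribution, the literature, or both, and leaves it optional. Sections 3.3.2 and 4.1 defer variable definitions to the SAP and specific tests to table shells. What can be said is that the cut is not pre-specified in the text reviewed.

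Finally, costs are not discarded as continuous data: means, medians and SDs are planned. The loss belongs to this one test.

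**Conclusion.** The point holds as a recommendation for improvement, not as a threat to the study's main result. The committed test of symptom burden against cost uses a high/low split at an open cut, and no full-scale alternative is firmly planned for cost, ED visits or inpatient stays.

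No single figure for the loss is warranted, because the plan gives neither the cut nor the number of variables to be cut. A headline of half the information lost would be too high for a median cut of cost alone and too low for a 2x2 table. The range is about 36% to 69% over the main settings, and somewhat more if a large majority of patients are high-symptom. A claim that a real association is likely to be missed holds only for weak ones: it fits a correlation near 0.10 but not 0.20 or above. All of this rests on normality of the symptom score and log cost, 770 evaluable patients and assumed correlations.

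**What to change.** In the Secondary Objectives paragraph of section 4.3:

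1. Analyse symptom burden against cost and utilization on the full scales. Use Spearman correlations of CAT total score and mMRC grade with a short named list, for example total all-cause cost, total COPD-related cost, and ED, inpatient and ambulatory counts.
2. Add a GLM for total cost (gamma, log link) and negative binomial models for the counts, with CAT total score as a continuous predictor. Section 4.5 already names GLM and negative binomial regression, though for the primary objective. State how zero costs are handled.
3. Label these analyses exploratory.
4. Keep cross-tabulations and chi-square tests for the categorical characteristics.
5. Show high/low cost by symptom group as description only, without a test, and fix the cut before the merge of survey and claims data described in section 3.1.6.
6. Reconcile the two CAT cut-offs before any grouped table is produced.

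The cost is wording in the SAP and table shells plus a few models on data already held; no new data are needed. The downside is a few more tables and several unadjusted exploratory tests, which is why the list should be short and named in advance. A model coefficient is also less easy to present than a high/low table.

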4.4 Inverse Probability of Treatment Weighting

To address the objective of comparing symptom burden of patients by treatment cohort (FLUT/SAL as compared to UMEC/VI), inverse probability of treatment weighting will be applied to reduce confounding on observed clinical, demographic, and sociodemographic characteristics shown in Appendix 4 (Section 11). The goal of adjusting for differences in non-treatment characteristics between treatment cohorts is to balance the distribution of covariates that would occur if participants were randomly assigned to treatment cohorts *a priori*.^{xiv} The weights in IPTW are based on each individual's probability of receiving a specific treatment given the confounders, which is known as the propensity score (PS). Use of methods that make adjustments via propensity scores is an appropriate way to create balance in the covariate distribution among cohorts.^{xv,xvi, xvii}

A logistic regression will be employed with a dependent or response that is conditioned on a set of predetermined covariates. Each subject will be assigned a propensity score weight and the adjustment for potential treatment selection bias will be made by weighting the expected value of an outcome or outcomes of interest in the corresponding multivariable model by a function of the inverse propensity score and sample size of the cohort.^{xviii}

The study team will examine the quality of the propensity score determination via descriptive techniques (e.g., examination of the overlap in histograms of the respective cohort propensity score distributions, and assessment of goodness of fit of the logistic regression) to ensure the weighting approach is sound. Following review of these diagnostics, the study team will identify the characteristics of any outliers and will determine whether those subjects should remain in the model based on their clinical and analytic characteristics and whether these characteristics would unduly impact subsequent multivariable analysis. The p values determined from the weighted and unweighted descriptive analysis of covariates included in the IPTW analysis will be compared.

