
	
count of COPD exacerbations combined with CAT total score and mMRC score. GOLD categories are mutually exclusive. Results will be presented overall and by treatment cohort (FLUT/SAL or UMEC/VI).
 
Multivariable modeling of the primary objective will be conducted following review of descriptive and IPTW results. Each model will examine the relationship between symptom burden and treatment with FLUT/SAL or UMEC/VI. The dependent variable for the models will be CAT total score and mMRC score, respectively; covariates for the models will be based on clinical and analytic significance.

Sample Size and Power
	
The study sample is estimated to include 385 patients per cohort with evidence of COPD diagnosis and single-inhaler dual therapy treatment with FLUT/SAL or UMEC/VI. A sample size of n=385 per cohort is required to assess statistical significance with a 95% confidence interval at ± 0.05 with 80% power. A sampling frame of 2,700 patients is estimated to be used to reach the target evaluable sample size, n=770 patients (385/cohort). Based on patient counts and response rate estimates, it is anticipated that two waves of data collection will be needed to meet the target sample size.
 
This estimated study sample size is sufficient to detect proportional differences in PRO outcomes between two cohorts of patients (i.e., patients treated with FLUT/SAL or UMEC/VI who have severe symptoms as measured by a CAT total score ≥ 10 or an mMRC score ≥ 2); other stratifications tied to primary and secondary endpoints may be considered for statistically powered analyses as sample size allows.

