3.5 Sample Size / Power Calculations

The sample size required for the study is based on several requirements. First, the study's primary outcome measures will be proportions (e.g., the proportion of patients experiencing symptoms who report low versus high symptom severity as measured by the mMRC and CAT total score). The estimated sample size is determined by the value and desired precision of the measured proportions.

Figure 6 displays the sample sizes required for various proportions, assuming a 95% confidence interval and a precision of ± 0.05 . Because the actual population proportions (e.g., the proportion of patients in each treatment cohort with mMRC scores ≥ 2 and the proportion of patients in each treatment cohort with CAT total scores ≥ 10) are unknown, the largest sample size indicated with that precision was selected. This largest value is for a proportion of 0.5 and assures a 95% confidence interval of ± 0.05 or

better for all proportions observed. Thus, a sample size of 385 completed patient surveys per treatment cohort was selected.

Figure 6 – Sample Sizes Required for Various Proportions

95% Confidence Interval	Proportion								
	0.9	0.8	0.7	0.6	0.5	0.4	0.3	0.2	0.1
±0.05	139	246	323	369	385	369	323	246	139

Since the proportion of patients experiencing symptoms will be determined from the survey and a variety of exclusion criteria can be applied only after data collection, a sampling frame of 2,700 patients is needed for an estimated evaluable sample size of 385 patients per treatment cohort. The sampling frame will be comprised of equal proportions per medication cohort (n=1,350 per cohort); however, proportional response rate by treatment cohort cannot be guaranteed. Based on the feasibility counts, Optum estimates that two waves of sample identification and survey data collection will be required to meet the target sample size. Sample identification for wave 2 will occur as soon as sufficient sample is available, which is estimated to be the month following wave 1 sample identification. The availability of the second wave will be assessed during protocol development.

Figure 7 – Estimated Final Evaluable Sample Size

Sampling frame per treatment cohort	n=1,350
Estimated response rate (30-35%)	405-470
Exclusion criteria applied following claims lag (2-5% ineligible)	8-24
Estimated final evaluable sample size per treatment cohort	385-446
Estimated total final evaluable sample size	770-892

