3.6 Hypotheses

The primary objective is to assess patient-reported COPD symptom burden among patients treated with UMEC/VI as compared to FLUT/SAL. The hypothesis for the primary objective is:

Null hypothesis:

- 1A) Patient-reported symptom severity as measured by CAT total score will not differ for UMEC/VI patients as compared to FLUT/SAL patients.
- 1B) Patient-reported symptom severity as measured by mMRC score will not differ for UMEC/VI patients as compared to FLUT/SAL patients.

Alternative hypothesis:

- 1A) Patient-reported symptom severity as measured by CAT total score will differ for UMEC/VI patients as compared to FLUT/SAL patients.
- 1B) Patient-reported symptom severity as measured by mMRC score will differ for UMEC/VI patients as compared to FLUT/SAL patients.

Hypotheses are presented for the primary objective since the sample size / power calculations are based on assessment of the primary objective.

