Depending on the distribution of the measure, the CAT and mMRC outcomes may be analyzed as a continuous or dichotomous measure. In general, continuous variables are analyzed using ordinary least square regression models. If transformed into a dichotomous measure (e.g., patients with a CAT total score > 10 or an mMRC score ≥ 2), the probability of an event will be modeled using logistic regression. Logistic regression models fit a maximum-likelihood logit model. Following standard procedure, regression diagnostics will be performed for each model to assess goodness of fit and violations of model assumptions (e.g., multicollinearity, heteroskedasticity). When there are violations of the model, they will be noted and appropriate corrections made to the data (i.e., typically through transformation of either the independent or dependent variables) or in the method of estimation. In addition, the fitted and the observed data will be examined to uncover outliers, their effect on the analysis, and possible misspecification of the initial equation.

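### The inverse-probability-weighted CAT and mMRC models have no stated variance estimator or weight formula, so default standard errors could give wrong p-values and intervals for UMEC/VI v FLUT/SAL.

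*Combined protocol and SAP*

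**What the plan says.** Section 4.4 estimates a propensity score by logistic regression and then adjusts by "weighting the expected value of an outcome or outcomes of interest in the corresponding multivariable model by a function of the inverse propensity score". The sentence goes on to make the weight depend on the cohort's sample size as well, but gives no formula, normalisation or truncation rule.

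Section 4.5 plans two models, one for CAT total score and one for mMRC score, each with treatment and covariates. For estimation it says "In general, continuous variables are analyzed using ordinary least square regression models" and, if a score is dichotomised, "Logistic regression models fit a maximum-likelihood logit model". It also lists GLM, Poisson and negative binomial regression as candidates.

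On departures from model assumptions, heteroskedasticity among them, Section 4.5 says that violations will be noted and corrected, "typically through transformation of either the independent or dependent variables". It then adds that the correction may instead be made in how the model is estimated. Robust, sandwich and bootstrap variances are not mentioned anywhere, nor is any allowance for the propensity score having been estimated.

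The hypotheses are two-sided. Alternative 1A in Section 3.6 reads "Patient-reported symptom severity as measured by CAT total score will differ for UMEC/VI patients as compared to FLUT/SAL patients", and 1B says the same for mMRC.

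**The concern.** Ordinary standard errors from a weighted regression misread propensity weights. Weighted least squares treats them as known precisions. A weighted likelihood treats them as counts of patients. They are neither, so a standard error that takes them at face value need not match the true sampling variability of the treatment difference.

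These models address hypotheses 1A and 1B, so the main p-values and intervals of the study are affected. There is a second route to harm. Section 4.4 compares weighted with unweighted p-values for the covariates, and Appendix 4 uses the weighted and unweighted results to choose the final covariates. An unsuitable weighted variance could therefore also influence which covariates enter the model.

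**Working it through.** **Inputs from the plan.** The target is 385 per cohort, 770 in total, with a 95% confidence level (Section 3.5) and two-sided hypotheses (Section 3.6). Covariates enter the outcome model in addition to the weights (Section 4.5).

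**Inputs not in the plan, so assumed.** These are the spread of the propensity score, how strongly covariates predict outcome, and the weight formula.

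**1. The plan's own figure.** Section 3.5 sizes each cohort "assuming a 95% confidence interval and a precision of ± 0.05", and says "This largest value is for a proportion of 0.5". So n = 1.96² × 0.5 × 0.5 / 0.05² = 384.1, rounded up to 385. This reproduces, as do the other entries in Figure 6. It is an unweighted, single-proportion calculation and makes no allowance for weighting.

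**2. Analytic check, normalised weights.** If weighting inflates the variance by a design effect D and the standard error ignores it, the nominal 5% test has type I error 2 × [1 − Φ(1.96/√D)].

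| D (assumed) | 1.96/√D | Type I error | Coverage of a nominal 95% interval |
|---|---|---|---|
| 1.10 | 1.869 | 0.062 | 93.8% |
| 1.25 | 1.753 | 0.080 | 92.0% |
| 1.50 | 1.600 | 0.110 | 89.0% |
| 2.00 | 1.386 | 0.166 | 83.4% |

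**3. Analytic check, unnormalised weights in a logit.** Raw inverse weights sum to about twice the sample (2 × 770 = 1,540). The reported standard error is then about 1/√(2D) of the true one.

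**4. Simulation under the null.** N = 770, 5 covariates, propensity score re-estimated in each of 2,000 replicates per setting. The propensity linear-predictor SD was 0.3, 0.6 or 1.0, and the covariate-outcome correlation was 0 or 0.5. Effective sample sizes were about 747, 694 and 578, so D = 770/747 = 1.03, 770/694 = 1.11 and 770/578 = 1.33. Near 5%, the Monte Carlo standard error is √(0.05 × 0.95/2000) = 0.005. Ranges are over the six settings.

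| Weighted model | Model-based SE ÷ true SD | Type I error, model-based | Type I error, sandwich |
|---|---|---|---|
| OLS, normalised, with covariates | 0.87-0.99 | 0.054-0.099 | 0.049-0.056 |
| Logit, normalised, with covariates | 0.86-0.99 | 0.050-0.097 | 0.043-0.059 |
| OLS, normalised, no covariates | 0.88-1.14 | 0.030-0.086 | 0.022-0.053 |
| Logit, normalised, no covariates | 0.86-1.08 | 0.035-0.093 | 0.024-0.055 |
| Logit, raw weights, no covariates | 0.61-0.76 | 0.134-0.229 | 0.024-0.055 |

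The formulas agree with the simulation where covariates do not predict outcome. At D = 1.33, 1/√1.33 = 0.87 (simulated 0.86-0.88) and 1/√(2 × 1.33) = 0.61 (simulated 0.61).

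**5. Sensitivity to the number of covariates.** With 20 covariates, 1,000 runs per setting and D of 1.11, 1.25 and 1.52, model-based type I error was as follows:

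- Weighted OLS with covariates: 5%, 8% and 10%.
- Normalised-weight logit with covariates: 6%, 8% and 10%.
- Raw-weight logit: 15%, 18% and 24% without covariates, and 19-25% with them.
- Sandwich variance: 2-6% throughout.

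A further 20-covariate simulation gave about 5-9% (normalised, with covariates), 15-23% (raw-weight logit) and 5-7% (sandwich, with covariates).

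**The case against.** The best defence is that silence is not a decision. Least squares and maximum likelihood describe how coefficients are estimated, and a sandwich or bootstrap variance is compatible with either. Section 4.1 leaves specific tests to separate table shells, and other details are deferred to a SAP that is not part of the text supplied. Section 4.5 also allows the estimation method to change. All of this stands against any claim that model-based errors will be used. It does not close the gap. Naming a test does not fix the variance of a weighted model, the protocol does not say that the weight formula or its variance is deferred, and the Section 4.5 remedy waits for a diagnostic to fail. The weighting problem exists whether or not one does.

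Three stronger readings are tempting, and the documents do not support them.

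- **A reader might infer that the intervals are bound to be too narrow.** The direction is not fixed. With prognostic covariates left out of the outcome model and mild or moderate propensity separation, normalised-weight model-based errors were too large (ratio 1.07-1.14, type I error 0.030-0.035). Section 4.5 does put covariates in, but which ones is undecided.
- **A reader might infer that the analysis will behave as if 1,540 patients had been surveyed.** That needs both a logit and unnormalised weights. Section 4.4 brings cohort sample size into the weight, which suggests scaling that may avoid the doubling. For OLS, multiplying all weights by one constant leaves the test unchanged.
- **A reader might infer that transforming CAT or mMRC has to be ruled out.** Hypothesis 1A says only that severity measured by CAT will differ. It does not fix a score-point estimand, so the scale of the result is a separate preference.

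**Conclusion.** The gap is real and concerns the error bars of the primary comparison. The plan weights the CAT and mMRC models but gives neither the weight formula nor a variance suited to it. If default model-based standard errors are used in the analysis closest to the plan (normalised weights plus covariates), they are typically somewhat too small. The false-positive rate is about 5-10% against a nominal 5%, and is negligible when the two cohorts have similar propensity scores. The 13-25% range applies only to unnormalised weights in a logit.

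All of these sizes rest on assumed propensity separation, covariate strength and weight form. They show what an unstated programming choice could do, and do not predict this study's result. A sandwich variance with covariates in the model kept the error near nominal throughout.

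**What to change.** In Sections 4.4 and 4.5:

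- Give the weight formula, and state that weights are normalised (stabilised) to the cohort sample size.
- State that every IPTW-weighted comparison uses a robust (sandwich) variance, or a bootstrap that refits the propensity model in each resample, in place of model-based standard errors. This should not depend on a diagnostic result, and should apply to whichever of the listed regression models is chosen.

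The cost is a few lines of text and standard SAS survey or GEE procedures, plus computing time if the bootstrap is chosen. Intervals will usually be slightly wider. The sandwich treats the weights as known and can be mildly conservative when prognostic covariates are not in the outcome model (type I error as low as 0.022 here). The wording should be settled before outcomes are seen.
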